12.6 Genomic Data Sharing Plan

Not applicable

13. STATISTICAL CONSIDERATIONS

13.1 Study Design/Endpoints

13.1.1 Overview

This is a phase 1 safety run-in and randomized phase 2 study designed to evaluate the safety and efficacy of the addition of anetumab ravidansine to pembrolizumab for patients with mesothelin positive malignant pleural mesothelioma. The study will utilize a randomized phase 2 study design to determine the anti-tumor activity of combination therapy with anetumab ravidansine and pembrolizumab (Group 2; experimental group) as compared to pembrolizumab alone (Group 1; control group), where response will be evaluated based on the modified pleural RECIST for pleural disease.

13.1.2 Primary Endpoint

The primary endpoint of the phase 1 safety run-in is the randomized phase 2 dose of anetumab ravidansine with combination of pembrolizumab.

The primary endpoint of the randomized phase 2 is the confirmed tumor response rate, which will be compared between the two groups. A confirmed tumor response rate defined as 100% times the number of eligible patients who have started the treatment and whose objective tumor status was a CR or PR on 2 consecutive evaluations at least 4 weeks apart (using RECIST v1.1 criteria) divided by the number of eligible patients who have started the treatment. All patients meeting the eligibility criteria who have signed a consent form, have been randomized and have begun treatment will be evaluable for overall response.

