11.1.2.2 Evaluable for Objective Response

All patients meeting the eligibility criteria who have signed a consent form, have been randomized and have begun treatment will be evaluable for response. These patients will have their response classified according to the definitions stated below

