11.1.7 Progression-Free Survival

PFS is defined as the duration of time from start of treatment until the first date that progressive disease is objectively documented or death from any cause, whichever occurs first.

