13.3 Sample Size/Accrual Rate

13.3.1 Sample Size

The phase 1 safety lead-in is expected to require a minimum of 12 patients and a maximum of 24 patients. The randomized phase 2 portion of this study is expected to require a minimum of 50 and a maximum of 98 evaluable patients. We anticipate accruing an additional 12 patients during the phase II portion of the trial to account for ineligibility, cancellation, major treatment violation, or other reasons. Therefore, the phase II portion is expected to accrue a maximum of 110 patients and overall sample size will be a maximum of 134 patients.

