13.5.2 Overall Survival

Overall survival is defined as the time from the start of treatment to death due to any cause. The distribution of survival time will be estimated using the method of Kaplan-Meier. The comparison of overall survival between two treatment arms will be based on the log-rank test.

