13.8.2 Evaluation of Response

All patients included in the study must be assessed for response to treatment, even if there are major protocol treatment deviations or if they are ineligible. Each patient will be assigned one of the following categories: 1) complete response, 2) partial response, 3) stable disease, 4) progressive disease, 5) early death from malignant disease, 6) early death from toxicity, 7) early death because of other cause, or 9) unknown (not assessable, insufficient data). [Note: By arbitrary convention, category 9 usually designates the “unknown” status of any type of data in a clinical database.]

All of the patients who met the eligibility criteria (with the possible exception of those

who received no study medication) should be included in the main analysis of the response rate. Patients in response categories 4-9 should be considered to have a treatment failure (disease progression). Thus, an incorrect treatment schedule or drug administration does not result in exclusion from the analysis of the response rate. Precise definitions for categories 4-9 will be protocol specific.

All conclusions should be based on all eligible patients. Sub analyses may then be performed on the basis of a subset of patients, excluding those for whom major protocol deviations have been identified (*e.g.*, early death due to other reasons, early discontinuation of treatment, major protocol violations, etc.). However, these sub analyses may not serve as the basis for drawing conclusions concerning treatment efficacy, and the reasons for excluding patients from the analysis should be clearly reported. The 95% confidence intervals should also be provided.

REFERENCES

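### Randomized eligible patients who never start treatment drop out of the response, PFS and OS comparisons, which leaves room for arm-dependent selection of unknown size and direction

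*Combined protocol and SAP*

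**What the plan says.** Section 13.1.2 restricts numerator and denominator alike: responders are "divided by the number of eligible patients who have started the treatment". It adds that patients who meet eligibility, have consented and "have been randomized and have begun treatment will be evaluable for overall response". Section 11.1.2.2 repeats the condition: "have been randomized and have begun treatment will be evaluable for response".

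The time-to-event definitions have the same starting point. Section 11.1.7: "PFS is defined as the duration of time from start of treatment until the first date that progressive disease is objectively documented", or death. Section 13.5.3 defines PFS the same way. Section 13.5.2: "Overall survival is defined as the time from the start of treatment to death due to any cause". A patient with no first dose has no time origin.

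Section 13.8.2 says two things. It asks for eligible patients to be in the main response analysis, with a possible exception for those "who received no study medication) should be included in the main analysis of the response rate". It then states "All conclusions should be based on all eligible patients", with no condition on starting.

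On how non-starting can arise, Section 4.4 gives 14 days from registration to first treatment and allows cancellation of a registration if no therapy is given. Section 8.1.3.1 has drug ordered only after randomization. Section 5.1 describes a control arm of pembrolizumab alone, without placebo. Note b of the study calendar limits eye examinations after screening to patients randomized to anetumab ravtansine. Section 13.3.1 provides for losses: "We anticipate accruing an additional 12 patients during the phase II portion of the trial to account for ineligibility, cancellation". That sentence goes on to include major treatment violations and other reasons.

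Section 13 contains no analysis of all randomized patients and does not ask for non-starters to be tabulated by arm.

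**The concern.** The phase 2 objective is superiority over a randomized control. Randomization protects that claim only while membership of the analysis set does not depend on what happens after allocation. Here it can. The arm can be known before the first dose, and a patient who then declines or is cancelled leaves the response comparison, PFS and OS together. If the patients who leave differ between arms in prognosis, the starters are no longer comparable. As the plan stands, the final report need not show how many left, from which arm or why, so a reader could not judge whether this happened.

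**Working it through.** **Inputs.** 49 evaluable patients per arm, response 20% against 40%, one-sided 0.10, final cut-off z > 1.282 and futility cut-off z < -0.072 at 25 per arm (Section 13.1.3.3); pooled-variance z-test (Section 13.2.2); maximum phase 2 accrual 110, which is 98 + 12 (Section 13.3.1).

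**The plan's own figure.** z = (pE - pC) / sqrt[p(1 - p)(1/nC + 1/nE)], with p the pooled rate. At 49 per arm and 20% against 40%, the normal approximation gives power 0.816. Exact binomial enumeration of the two-stage design gives 0.817, against 0.80 in the text and 0.805 in the table. Exact one-sided error at 20% in both arms is 0.097 without the futility look and 0.095 with it. (The table's entry for zero difference, 0.009, does not match this; it is a separate matter and is not used here.)

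**Scenarios.** Assumptions, none of them from the documents: 55 randomized per arm (110/2), true response 20% in both arms, d patients in an arm never start, and they would have responded at rate q. The starters' rate is (55 × 0.20 - d × q)/(55 - d). For d = 6 and q = 0.40 this is (11 - 2.4)/49 = 17.6%; for d = 6 and q = 0 it is 11/49 = 22.4%. Errors are exact, without the futility look; the look lowers the starters-only error by less than 0.01. The last column analyses all randomized patients with every non-starter counted as a non-responder.

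| Non-starters | Would-be response | Starters, control / combination | Error, starters only | Error, all randomized |
|---|---|---|---|---|
| 6 control | 40% | 17.6% / 20.0% | 0.172 | 0.246 |
| 3 control | 40% | 18.8% / 20.0% | 0.133 | 0.161 |
| 6 control | 20% | 20.0% / 20.0% | 0.103 | 0.160 |
| 6 combination | 0% | 20.0% / 22.4% | 0.165 | 0.100 |
| 6 combination | 40% | 20.0% / 17.6% | 0.059 | 0.030 |
| 6 in each arm | 40% | 17.6% / 17.6% | 0.099 | 0.099 |
| 6 in each arm | 20% | 20.0% / 20.0% | 0.097 | 0.097 |

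The fourth column shows that the error moves only when departures differ by arm and are related to prognosis, and that it can move either way. The last column shows that counting non-starters as failures restores the error when would-be non-responders leave the combination arm. It makes matters worse when the non-starters are in the control arm.

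**Sensitivity of one result.** With 10/49 control responders, the smallest winning combination count is 16/49: z = (0.3265 - 0.2041)/sqrt[0.2653 × 0.7347 × 2/49] = 1.373. Adding two combination non-starters as non-responders gives 16/51: z = (0.3137 - 0.2041)/sqrt[0.26 × 0.74 × (1/49 + 1/51)] = 1.250, below 1.282.

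**Power with everyone counted.** With 6 non-starters per arm as failures, the rates become 0.20 × 49/55 = 17.8% and 0.40 × 49/55 = 35.6%. At 55 per arm, power is 80.2% by normal approximation and 81.7% exactly, with one-sided error 0.097.

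**The case against.** Several points on the other side stand.

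- The size is assumed. No section gives a refusal rate, an imbalance between arms or a link with prognosis. The 12 extra patients cover all reasons in both arms, so six refusals in one arm would use half of that allowance.
- The mechanism is partly inferred. The documents do not use the term open-label, and Section 4.4 does not mention refusal after the arm is known. Section 5.1.2 allows pembrolizumab up to 5 days after randomization, which suggests a shorter gap than 14 days. The lack of placebo and the arm-specific procedures still make knowledge of the arm a fair inference.
- Section 13.8.2 covers much of the ground. Treatment deviations stay in the response analysis, and early deaths and unknown outcomes count as failures. Only eligible non-starters are left unsettled.
- A started-treatment set is common in phase 2 activity trials, and a positive result here leads only to further testing. PFS and OS are secondary analyses, and OS is not among the Section 1.2 objectives. No effect on either has been quantified.

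A reader might go further and infer that the comparison is biased in favour of the combination, or that the sponsor expects 11% (12/110) never to start. The documents support neither: the direction is unknown and the allowance is not a non-start rate. A reader might also infer that an all-randomized analysis with non-starters as non-responders would settle the matter. It would not: with six control non-starters that analysis has error 0.16 to 0.25.

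**Conclusion.** The gap is real. Eligible randomized non-starters are outside the response, PFS and OS comparisons, Sections 11.1.2.2 and 13.1.2 disagree with part of Section 13.8.2 about them, and nothing requires them to be counted or shown by arm. The resulting bias is possible, not demonstrated. Under the assumed scenarios with six non-starters in one arm, the nominal 0.10 one-sided error ranges from about 0.06 to 0.17; it stays near 0.10 if non-starting is unrelated to prognosis or is the same in both arms. This does not make the started-treatment set an invalid primary set, and it does not show that the trial's error rate is inflated. It is a low-cost improvement worth making before the final analysis.

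**What to change.** Keep the treated-eligible set as the primary response analysis if preferred, and make these changes:

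- Define PFS and OS from randomization in all randomized eligible patients. Follow non-starters for vital status, and for progression where possible; Section 5.6 currently ties follow-up to removal from study treatment.
- Report non-starters by arm, with reasons.
- Reconcile Sections 13.1.2 and 11.1.2.2 with Section 13.8.2 on whether eligible non-starters count.
- Prespecify an all-randomized response sensitivity analysis with non-starters handled in at least three ways: as non-responders in both arms; at the control-arm response rate; and in a worst case against the combination (control non-starters as responders, combination non-starters as non-responders). Show the results together, since no single assumption is protective in every pattern of non-starting.

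The cost is SAP wording, follow-up of a few patients and a small extra analysis. No patients need be added: with six non-starters per arm counted as failures among 110 randomized, power stays at about 80% to 82%.

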13.1.3 Statistical Design

13.1.3.1 Phase 1 Safety Run-In

A phase 1 safety run-in will be performed after the first 6 patients have been accrued to the safety lead-in portion of the study at dose level 1 and observed for one cycle. If 2 or more of the first 6 patients experience a DLT as defined in Section 5.2.1, then the starting dose level will be adjusted and additional cohorts may be evaluated at dose levels -1 and -2 as described below. Accrual will be halted while evaluating each cohort in the safety lead-in analysis.

- Dose level 1: Six evaluable patients will be accrued onto dose level 1 and observed until they complete two cycles of treatment. If 0 or 1 out of 6 patients experience a DLT, accrual will continue in the phase 2 portion at dose level 1 after the expansion cohort per Section 13.2.2. If 2 or more patients experience a DLT on dose level 1, the toxicity level for dose level 1 will be considered unacceptable and six additional patients will be treated on dose level -1.
- Dose de-escalation to dose level -1: If dose level 1 has an unacceptable level of toxicity, six evaluable patients will be accrued onto dose level -1. If 0 or 1 out of 6 patients experience a DLT on dose level -1, accrual will continue in the phase 2 portion at dose level -1 after the expansion cohort per Section 13.2.2. If 2 or more patients experience a DLT, the toxicity level for dose level -1 will be considered unacceptable and six additional patients will be treated on dose level -2.
- Dose escalation to dose level -2: If dose level -1 has an unacceptable level of toxicity, six evaluable patients will be accrued onto dose level -2. If 0 or 1 out of 6 patients experience a DLT on dose level -2, accrual will continue in the phase 2 portion at dose level -2 after the expansion cohort per Section 13.2.2. If 2 or more patients experience a DLT, the toxicity level for dose level -2 will be considered unacceptable and accrual to the study will be temporarily closed, evaluated and potentially amended.

The simulations below demonstrate the chance of the design to select a dose with an acceptable probability of DLT of 0.2.

	Dose Level				
	1 (6.5 mg/kg)	-1 (5.5 mg/kg)	-2 (4.5 mg/kg)	No selection %	Ave # of pts
True DLT rate	0.2	0.1	0.05		
Select %	68	30	2	0	8.04
# pts treated	6	1.92	0.12		
True DLT rate	0.4	0.2	0.1		
Select %	31	49	18	2	11.34
# pts treated	6	4.14	1.20		
True DLT rate	0.5	0.4	0.2		
Select %	14	19	43	24	15.18
# pts treated	6	5.16	4.02		

13.1.3.2 Expansion Cohort

Once the final dose level is determined, an additional 6 patients will be enrolled to the final dose level to ensure safety. If 2 or less out of the 12 patients experience a DLT, this dose level will be determined as the safe dose for the randomized phase 2 study. If 3 or more than 3 patients experience a DLT, this dose level will be considered unacceptable and accrual to the study will be temporarily closed, evaluated and potentially amended. With a maximum of 12 patients at the randomized phase 2 dose, the probability of observing at least one grade 3 or higher AE is 86% when the true

rate of such AE is 15% for the combination arm.

13.1.3.3 Randomized Phase 2 Study

Decision Rule: A randomized phase 2 trial comparing combination therapy with anetumab ravidansine and pembrolizumab as compared to pembrolizumab alone will be conducted, once a safe combination of doses is identified. We will enter 49 evaluable patients on each arm (98 total) of the study using a 1:1 randomization scheme utilizing the permuted block procedure, where patients are stratified based on ECOG performance score (0 vs. 1). A sample size of 49 patients per arm provides 80% power to detect an improvement in response rate from 20% to 40%, using a one-sided test at a significance level of 0.10. The baseline response rate of 20% is based on a prior study⁷³. In addition, this trial implements a group sequential design with a single interim analysis, adopting the Rho family (Rho=2) beta spending function for controlling the overall type II error rates. The interim and final analysis boundaries and characteristics were generated using the East 6 clinical trial software program (version 6.4, Cytel Inc.).

The Z-score will be calculated for testing the null hypothesis that the difference of response rates between two arms is equal to zero, based on the normal approximation with pooled variance of standardized test statistics. The study design will be implemented as follows:

Interim Analysis Decision Rule: An interim analysis will be performed for futility. After the first 25 patients randomized into each arm (the first 50 patients in both arm) become evaluable for the primary endpoint, if the z-score is less than -0.072, we will terminate accrual and consider this early evidence that the experimental arm does not have a higher overall response rate and accrual will be terminated. Otherwise, we will continue accrual.

Final Decision Rule: If the interim analysis criteria are met for full accrual, a total of 49 evaluable patients per arm will be enrolled into this study. At the final analysis, it will be concluded that the experimental arm (combination therapy) is superior to the control arm (pembrolizumab alone), if the z-score is greater than 1.282. This will be considered sufficient evidence that the experimental arm may be recommended for further testing in subsequent studies. Otherwise, we will conclude that there is no statistical evidence of superiority of the experimental regimen (combination therapy).

Over Accrual: If more than the target number of patients are accrued, the additional patients will not be used to evaluate the stopping rule or used in any decision making process however, they will be included in final point estimates and confidence intervals.

NOTE: The trial will not be halted while the first 25 patients in each group are evaluated for the interim analysis. However, if the accrual is especially rapid, we may temporarily suspend accrual to prevent missing important acute toxicity patterns.

Other Considerations: Toxicity, quality/duration of response, and patterns of treatment failure observed in this study, as well as scientific discoveries or changes in standard care will be taken into account in any decision to terminate the study.

Power and Significance Level: Assuming that the response rate is binomially distributed in each group, the operating characteristics of the current design can be tabulated according to various true difference of the proportions, including the probabilities of the experimental arm (combination therapy) is superior to control arm (pembrolizumab alone), i.e. power which warrants further studies on experimental regimen, and probabilities of stopping the trial early due to futility of the experimental regimen.

If the true difference of proportion is	-0.1	0	0.1	0.2	0.3
Then the probability of declaring that the experimental regimen warrants further studies is...	0.004	0.009	0.424	0.805	0.970
*Probability of stopping at the interim analysis due to futility is...	0.805	0.458	0.183	0.051	0.009

*Probabilities are based on simulation study with 50,000 replicates

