13.2.2 Randomized Phase 2 Primary Endpoint Estimation

The proportion of successes will be estimated in each group by the number of successes

divided by the total number of evaluable patients. Confidence intervals for the true success proportion will be calculated in each arm. Comparison of confirmed response rates between the two treatment groups will be performed using a one-sided z-test with pooled variance at significance level 0.10.

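### The phase 2 operating-characteristics table prints 0.009 as the false-positive probability; the stated decision rule gives about 0.095

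*Combined protocol and SAP*

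**What the plan says.** Section 13.1.3.3 (Randomized Phase 2 Study) sets up the comparison "using a one-sided test at a significance level of 0.10". The sample size is given as: "We will enter 49 evaluable patients on each arm (98 total) of the study using a 1:1 randomization scheme". On the control rate it says: "The baseline response rate of 20% is based on a prior study". The test statistic is a z-score for the difference in response rates, "based on the normal approximation with pooled variance of standardized test statistics". There is one futility look at 25 patients per arm, with accrual ending if z is below -0.072. At the final analysis the combination is declared superior "if the z-score is greater than 1.282". Section 13.2.2 repeats the level, calling for a "one-sided z-test with pooled variance at significance level 0.10".

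The table under Power and Significance Level, at the end of section 13.1.3.3, then reports the following.

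| True difference | -0.1 | 0 | 0.1 | 0.2 | 0.3 |
|---|---|---|---|---|---|
| Declare worth further study | 0.004 | 0.009 | 0.424 | 0.805 | 0.970 |
| Stop for futility | 0.805 | 0.458 | 0.183 | 0.051 | 0.009 |

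The label of the first row begins: "Then the probability of declaring that the experimental regimen warrants further studies is".

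**The concern.** At a true difference of 0, the first row of the table is the chance of a positive trial when the combination adds nothing to pembrolizumab. The final cut-off of 1.282 is the one-sided 0.10 point of the normal distribution, and the only early stop is for futility with a boundary close to zero. Such a stop removes few trials that would later have crossed 1.282. The attained error should therefore lie just under 0.10, not under 0.01.

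A positive result is the plan's basis for recommending further testing of the combination. A reader who takes the table at face value would believe that such a result arises by chance less than 1% of the time, when the rule allows nearly 10%.

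**Working it through.** **Inputs, all from section 13.1.3.3.** Interim n = 25 per arm; final n = 49 per arm; futility if z < -0.072; success if z > 1.282; pooled-variance z; binomial responses; control rate 20%. The table does not state the control rate behind each column. The 20% used in the sample-size statement is taken, and then varied.

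**Sample size first.** The usual formula for 20% versus 40%, one-sided 0.10, 80% power and no interim look gives 47 per arm, and 49 per arm gives power 0.816. The stated 49 per arm and 80% power therefore reproduce.

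**Exact two-stage calculation.** With x responders on control and y on the combination, each out of n,

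z = (y/n - x/n) / sqrt(2p(1 - p)/n), where p = (x + y)/(2n).

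All outcomes of Bin(25) × Bin(25) with z ≥ -0.072 are carried forward and convolved with Bin(24) × Bin(24). The probability of final outcomes with z > 1.282 is then summed.

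| True difference | -0.1 | 0 | 0.1 | 0.2 | 0.3 |
|---|---|---|---|---|---|
| Printed | 0.004 | **0.009** | 0.424 | 0.805 | 0.970 |
| Exact | 0.004 | **0.095** | 0.440 | 0.817 | 0.969 |
| Normal approximation | 0.0035 | **0.096** | 0.436 | 0.813 | 0.973 |

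The normal approximation at difference 0 is P(Z1 > -0.072 and Z2 > 1.282) with correlation sqrt(25/49) = 0.714, which is 0.0961. Without the interim look the tail area beyond 1.282 is 0.0999, so the futility stop removes only about 0.004. A simulation of 500,000 trials gave 0.0952 at difference 0. The ratio of exact to printed is 0.0951/0.009 = 10.6, or about 10.5 from the rounded 0.095.

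**Other readings of the rule at difference 0:**

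- Common response rate 5/10/15/20/25/30/40/50%: 0.116/0.103/0.098/0.095/0.098/0.102/0.091/0.092.
- No futility look (exact): 0.097.
- Unpooled variance: 0.104.
- Interim at 24 per arm: 0.095.
- Arm sizes allowed to vary under stratified permuted blocks: 0.095, 0.097 and 0.097 for blocks of 2, 4 and 6. Block sizes and a 50:50 split of the strata are assumptions, since the plan gives neither.
- Simulation noise: the standard error at 50,000 replicates is sqrt(0.095 × 0.905/50,000) = 0.0013, against a gap of 0.095 - 0.009 = 0.086.

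**A stricter cut-off.** Moving the final cut-off to 2.35 gives 0.0088 at difference 0. Power at difference 0.2 then falls to 0.433, against the printed 0.805. No single final cut-off produces both printed values.

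**Check within the printed row.** On the normal-quantile scale the five printed values are -2.65, -2.37, -0.19, 0.86 and 1.88, so successive steps are about 0.29, 2.17, 1.05 and 1.02. Replacing 0.009 by 0.095 (quantile -1.31) gives steps of 1.34, 1.12, 1.05 and 1.02, a smooth curve. Only the entry at 0 breaks the pattern.

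**The case against.** Four points can be made on the other side.

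- **A misread digit.** The text reviewed was extracted from PDF by a program, so a dropped or misread digit (0.09 or 0.099, say) cannot be ruled out. This stands as a caveat. Nothing positively suggests a misread, though, since the neighbouring entries read cleanly.
- **A level is an upper bound.** An attained error of 0.009 would not breach a 0.10 level. That is right as far as it goes, and the conflict with 0.10 alone would not settle the matter. The decisive conflict is with the 1.282 cut-off and with the rest of the row, which no rule giving 0.009 can reproduce.
- **The other entries are not exact either.** The exact futility row is 0.790, 0.429, 0.161, 0.042 and 0.007, so the printed values differ by up to 2.9 points (0.458 against 0.429). Gaps of that size exceed simulation error, so the table was probably not produced by exact enumeration. The normal approximation gives 0.823, 0.471, 0.186, 0.049 and 0.008, which is generally closer. Differences of 1 to 3 points are what a change of method would produce; a tenfold difference in one entry is not.
- **Nothing operational depends on the entry.** The level and the cut-off are stated correctly where they govern conduct. That limits the consequence. It does not make the entry harmless, because it is the plan's tabulated type I error, under a heading that announces it.

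**Conclusion.** The concern holds. As the table reads in the supplied text, the probability of a false-positive declaration is 0.009, while the plan's own rule gives 0.095 (0.096 by normal approximation), a factor of about 10.5. The result assumes a 20% response rate in both arms but hardly depends on it: rates from 5% to 50% give 0.091 to 0.116. The size and isolation of the discrepancy point to a dropped or misplaced digit, but the documents do not confirm the cause. This should be fixed. It is a reporting error in one entry and leaves the sample size, boundaries, power and conduct of the trial as they are.

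**What to change.** Compare the difference-0 entry with the source document and with the design-software output that generated the boundaries. If 0.009 is what the protocol prints, replace it with the software value, which should be close to 0.095; that figure is this review's recalculation, and a value nearer 0.096 would be expected if the software used the normal approximation. The remaining entries can stay. It would also help to state beside the table that the control rate is 20% and how the declaration row was calculated, since the simulation footnote is attached only to the futility row. The cost is one table entry and a line of text, with no change to design or conduct.

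### The futility-stopping probabilities tabulated for phase 2 do not come from the written 25-per-arm rule; they overstate the chance of stopping by up to 2.9 points

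*Combined protocol and SAP*

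**What the plan says.** All of this is in section 13.1.3.3 of the combined protocol and SAP.

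- **Timing of the look:** "After the first 25 patients randomized into each arm (the first 50 patients in both arm) become evaluable for the primary endpoint". The note on not halting accrual repeats 25 patients in each group.
- **Stopping rule:** "if the z-score is less than -0.072, we will terminate accrual", with the z-score "based on the normal approximation with pooled variance of standardized test statistics".
- **Design:** "We will enter 49 evaluable patients on each arm (98 total) of the study using a 1:1 randomization scheme". This "provides 80% power to detect an improvement in response rate from 20% to 40%, using a one-sided test at a significance level of 0.10". On the control rate: "The baseline response rate of 20% is based on a prior study".
- **Final test:** superiority is concluded "if the z-score is greater than 1.282".
- **Operating characteristics:** responses are taken as binomial in each group. The futility row reads 0.805, 0.458, 0.183, 0.051 and 0.009 for true differences of -0.1, 0, 0.1, 0.2 and 0.3. Its footnote says "Probabilities are based on simulation study with 50,000 replicates".

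**The concern.** With equal arms, a tie in responders gives z = 0 and the trial continues. Stopping therefore requires the combination arm to have strictly fewer responders. If the two true rates are equal, each arm is equally likely to be the one behind, and ties take a share, so the stopping probability must be clearly below one half. The tabulated 0.458 looked too high for that.

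The row is the plan's only statement of how often the interim look ends the trial when the combination adds nothing or does harm. A monitoring board or ethics reviewer would take it as describing the rule in force. If it was simulated on a different interim sample, it describes another rule and makes the protection look slightly better than it is.

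**Working it through.** **Inputs (all from section 13.1.3.3).** Interim size 25 per arm; stop if pooled z < -0.072; binomial responses; control rate 0.20; 49 per arm at the end; success if z > 1.282; 50,000 simulated trials. The table does not name its control rate. I use the 20% on which the design is based, so the combination rate is 0.20 + difference.

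**The basic design reproduces.** Per-arm sample size by the usual formula for 20% versus 40%, one-sided 0.10, power 80%:

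[1.2816·√(2·0.3·0.7) + 0.8416·√(0.2·0.8 + 0.4·0.6)]² / 0.2² = (0.8306 + 0.5323)² / 0.04 = 46.4, so 47.

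The planned 49 gives about 0.816. Exact two-stage power with a 25/25 futility look is 0.817, against 0.805 in the table. Sample size and power are sound.

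**What the written rule means.** With X responders of 25 on the combination, Y of 25 on control and p̂ = (X + Y)/50,

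z = (X/25 − Y/25) / √(p̂(1 − p̂)·2/25).

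A tie gives z = 0. One fewer responder on the combination gives its z closest to zero when p̂ is 0.5: −0.04/√(0.25·0.08) = −0.283, already below −0.072. So the rule is: stop if X < Y.

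**Ceiling under equal rates.** By symmetry P(X < Y) = (1 − P(tie))/2.

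| Common rate | P(tie) | P(stop) |
|---|---|---|
| 0.1 | 0.1909 | 0.405 |
| 0.2 | 0.1412 | 0.429 |
| 0.3 | 0.1227 | 0.439 |
| 0.4 | 0.1146 | 0.443 |
| 0.5 | 0.1123 | 0.444 |

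Over common rates from 0.02 to 0.98 the maximum is 0.444, at 0.5. The stated 0.458 is above it, so no choice of control rate produces that entry.

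**Whole row, by exact enumeration of the two binomials.**

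| True difference | −0.1 | 0 | 0.1 | 0.2 | 0.3 |
|---|---|---|---|---|---|
| Stated | 0.805 | 0.458 | 0.183 | 0.051 | 0.009 |
| 25 per arm (written rule) | 0.7898 | 0.4294 | 0.1611 | 0.0415 | 0.0070 |
| Stated minus exact, points | 1.5 | 2.9 | 2.2 | 0.9 or 1.0 | 0.2 |
| 25 control, 24 combination | 0.8031 | 0.4568 | 0.1837 | 0.0518 | 0.0098 |
| 24 control, 25 combination | 0.7859 | 0.4799 | 0.2164 | 0.0656 | 0.0126 |

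**Simulation error.** The standard error is √(p(1 − p)/50,000): 0.0022 at 0.458 and 0.0004 at 0.009. Allowing also for rounding to three decimals, the stated values lie 8.5, 12.7, 12.5, 9.3 and 3.9 standard errors above the 25-per-arm values.

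**Which look fits.** Over all pairs of arm sizes from 20 to 30, 25 control with 24 combination fits best: the sum of squared standardised differences over the five columns is 4.7, and every column is within about 0.2 point. Next is 26 control with 25 combination, at 14.8. The written 25/25 gives 491.

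**The row above.** Exact probabilities of declaring the regimen worth further study, with the 25/25 look and 49 per arm at the end, are 0.004, 0.095, 0.440, 0.817 and 0.969. The table has 0.004, 0.009, 0.424, 0.805 and 0.970. The second entry is about a tenth of the exact value. A 25/24 look gives 0.094 there, so interim arm size does not explain that cell.

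**The case against.** The strongest counter-case has four parts.

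- **The cause is inferred.** The documents do not give the arm sizes used in the simulation, and 26 control with 25 combination is within about half a point in every column. This stands: 25/24 is a description of the fit, not an established fact. The discrepancy does not depend on it, because the 0.444 ceiling already rules out 0.458 under the written rule.
- **The normal approximation is close.** At 25 per arm it gives 0.823, 0.471, 0.186, 0.049 and 0.008, within 2 points of every stated value. But the plan attributes the row to binomial simulation, and the approximation misses the zero-difference entry by 1.3 points, about 6 standard errors.
- **Real splits may not be 25/25.** Stratified permuted blocks need not divide the first 50 patients equally, and small imbalances move the figure more than the error does: under no effect, 0.485 with 26 control and 24 combination, and 0.514 with the reverse. True, but the rule fixes 25 in each arm, and the table should describe that rule.
- **It is small.** No boundary, sample size or decision changes, and 43% rather than 46% would hardly alter anyone's judgement. This stands and sets the weight of the point. The 0.009 entry in the row above is the larger error in the same table.

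**Conclusion.** The concern holds. The stated futility probabilities are not those of the written 25-per-arm rule. They overstate the chance of stopping in every column, most at no true difference: 0.458 against 0.429, or 2.9 points. The excess is 1.5 points when the combination is 10 points worse and 1 point or less at differences of 0.2 and 0.3.

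The row-wide figures assume a 20% control rate and exactly 25 evaluable patients per arm. The statement that 0.458 is unattainable needs only equal arms of 25 and equal true rates. That the simulation used 25 control and 24 combination patients is an inference from the fit. The matter is minor: it concerns the reported operating characteristics, not the conduct of the trial.

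**What to change.** Replace the stopping row with the exact values for 25 per arm and a 20% control rate: 0.790, 0.429, 0.161, 0.0415 and 0.007. State the control rate and interim arm sizes under the table. Recompute the row above on the same rule (0.004, 0.095, 0.440, 0.817, 0.969), which also corrects the 0.009 at zero difference. If the simulation deliberately used unequal arms, say so and reconcile that with the interim decision rule.

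The cost is table values and a footnote. The only visible consequence for the stopping row is a slightly less favourable figure under no effect, 43% instead of 46%.
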